6.9.4.2. Reporting SAEs – Procedure for Investigators

Initial Reports

SAEs, regardless of causality assessment, must be collected beginning from the time the subject signs the study consent until the last study visit or 30 days after the last dose of study drug, whichever is longer. All SAEs must be reported to Medpace Clinical Safety **within 24 hrs** of the knowledge of the occurrence (this refers to any adverse event that meets any of the aforementioned seriousness criteria). Any SAE judged by the Investigator to be related to the study treatment should be reported to the Sponsor regardless of the length of time that has passed since study completion.

To report the SAE, complete the SAE form electronically in the electronic data capture (EDC) system for the study. When the form is completed, Medpace Safety personnel will be notified electronically and will retrieve the form. If the event meets seriousness criteria and it is not possible to access the EDC system, send an email to Medpace Safety at [contact] or call the Medpace SAE hotline (phone number listed below) and fax or email the completed paper SAE form to Medpace (fax number/email address listed below) within 24 hrs of awareness. When the EDC system becomes available, the SAE information must be entered within 24 hrs of the system becoming available.

It is very important that the SAE electronic case report form be filled out as completely as possible at the time of the initial report, including if possible the Investigator's assessment of causality. The minimum information needed for making a preliminary SAE report is the protocol number, the subject ID, an adverse event term and the name of the person reporting the information to the Sponsor. Preliminary SAE reports should be followed as soon as possible by detailed descriptions including copies of hospital case reports, autopsy reports and other documents requested by the Sponsor (see Follow-up Reports, below).

Medpace Clinical Safety Contact Information:

Medpace SAE hotline – USA:
[contact], [name] **or** [contact], [name]
[contact] **or** [contact]
e-mail: [contact]

Medpace SAE hotline – Europe:
[contact]
[contact]
e-mail: [contact]

Follow-up Reports

All AEs and SAEs must be followed to resolution or, if resolution is unlikely, to stabilization.

Within 24 hrs of receipt of follow-up information, the Investigator must update the SAE form electronically in the EDC system for the study and submit any supporting documentation (e.g., subject discharge summary or autopsy reports) to Medpace Clinical Safety via fax or e-mail. If the follow-up information changes the Investigator's assessment of causality, this should also be noted on the follow-up SAE form. If it is not possible to access the EDC system, refer to the procedures outlined above for initial reporting of SAEs.

The Investigator should notify the IRB/EC of the occurrence of the SAE, in writing, in accordance with local requirements.

6.9.5. Pregnancy Reporting

Any pregnancy following study drug dosing where the estimated date of conception occurred either prior to the study termination visit or within 30 days of last study treatment must be reported. The Investigator should report the pregnancy to Medpace Clinical Safety within 24 hrs of being notified. Medpace Clinical Safety will then forward the Exposure *In Utero* form to the Investigator for completion. **The contact information for reporting pregnancies is the same as for reporting SAEs (Section 6.9.4.2).**

A subject becoming pregnant while on study drug will immediately be withdrawn from the study and early termination study procedures will be performed.

The subject should be followed by the Investigator until completion of the pregnancy. If the pregnancy ends for any reason before the anticipated date, the Investigator should notify Medpace Clinical Safety. At the completion of the pregnancy, the Investigator will document the outcome of the pregnancy. If the fetus has a congenital anomaly, the Investigator should follow the procedures for reporting an SAE.

6.9.6. Regulatory Reporting of Adverse Events

AEs will be reported to the regulatory authorities in compliance with local and regional law and established guidance by the Sponsor or by a third party acting on behalf of the Sponsor. The format of these reports will be dictated by the local and regional requirements.

6.10. Laboratory Tests

Blood, urine and saliva samples for assessments of efficacy, safety and PK will be obtained as shown in the study schedule in [Appendix 1](#). Please see the Laboratory Manual for blood collection volumes. Testing of clinical laboratory samples will be carried out by the central clinical laboratory and will include the tests listed in [Table 3](#). Testing of PK samples will be carried out by the central PK laboratory. Samples may also be assessed for other parameters relevant to steroid metabolism. Subjects need to fast from 10 PM (22:00; water and maintenance medications allowed) the evening prior to Visits S1, R1 and R3/ET. Subjects need to be in a seated position for at least 15 minutes prior to collection of blood hormone levels so that renin and aldosterone levels are stable. For other blood tests, subjects may be seated or supine.

For all female subjects of childbearing potential, a serum pregnancy test will be performed via the central laboratory at screening (Visit S1) and a urine pregnancy test will be performed at the study site (preferred; however, if required by the institution/IRB/EC, a serum or urine sample may be submitted to a laboratory for pregnancy testing instead) at all subsequent study visits.

Abnormal, clinically significant results may be verified to rule out laboratory error. Persistent relevant abnormal values must be followed up until the cause is determined or until they return to the baseline value. Abnormal laboratory findings that are considered clinically significant by the Investigator should be recorded as AEs as appropriate (Section [6.9](#)).

Table 3: List of Clinical Laboratory Tests

Hematology	hematocrit (Hct), hemoglobin (Hgb), platelet count, red blood cell (RBC) count, white blood cell (WBC) count with differential
Chemistry	albumin (ALB), alkaline phosphatase (ALK-P), alanine aminotransferase (ALT; SGPT), aspartate aminotransferase (AST; SGOT), blood urea nitrogen (BUN), calcium (Ca), creatinine (including calculated glomerular filtration rate), glucose, total bilirubin, total protein, electrolytes (magnesium, sodium, potassium, chloride, bicarbonate)
Coagulation	PT, aPTT, INR
Metabolic	insulin, HbA1c, lipid panel (total cholesterol, LDL, HDL, triglycerides)
Hormones	11-DOC, 17-OHP, A, A4, ACTH, cortisol, DHEA, DHEAS, free T, P, renin, SHBG, total T
Urinalysis	appearance, bilirubin, color, glucose, ketones, microscopic examination of sediment, nitrite, occult blood, pH, protein, specific gravity, urobilinogen
Other	HBsAg, HCV, HIV, serum and urine pregnancy tests, urine drug screen, UFC (including total volume and total creatinine), salivary cortisol

11-DOC, 11-deoxycorticosterone; 17-OHP, 17-hydroxyprogesterone; A, aldosterone; A4, androstenedione; ACTH, adrenocorticotrophic hormone; aPTT, activated partial thromboplastin time; DHEA, dehydroepiandrosterone; DHEAS, dehydroepiandrosterone sulfate; HbA1c, hemoglobin A1c; HBsAg, hepatitis B surface antigen; HCV, hepatitis C virus; HDL-C, high-density lipoprotein cholesterol; HIV, human immunodeficiency virus; INR, international normalized ratio; LDL-C, low-density lipoprotein cholesterol; P, progesterone; PT, prothrombin time; SHBG, sex hormone binding globulin; T, testosterone; UFC, urinary free cortisol

6.10.1. Efficacy Assessments

6.10.1.1. 24-Hour Urinary Free Cortisol

24-hr urine collections for assessment of UFC will be performed using the standard procedure (see Laboratory Manual). If a urine collection is suspected to be incomplete, a repeat 24-hr UFC may be performed with approval of the Medical Monitor.

Two collections will be done during the screening period, within 28 days prior to enrollment into the open-label dose-escalation period (Visit T1), and results reviewed for eligibility prior to enrollment. Subjects who require wash-out of medications should perform these collections AFTER wash-out.

During the Open-Label Dose-Escalation Period of the study, subjects will begin a 24-hr urine collection on Days 13, 14, 27, 28, 41, 42, 50, 51, and 56. In addition, subjects in the Double-Blind Randomized Withdrawal Period of the study will begin a 24-hr urine collection on Days 64, 65, 79, and 84; and subjects in the Additional Open-Label Dosing Period of the study will begin a 24-hr urine collection on Days 69, 70, 79, and 84. The collections that occur within 2 days before study visits should be brought to the corresponding study visit (along with any other samples that had not been previously submitted). For all other collections, when completed, a visiting nurse may assist with processing and shipping these 24-hr collections to the central laboratory, or the subject may submit them to the study site, per subject preference.

The mean of the Day 50 and the Day 51 (“mean Day 50/51”) 24-hr UFC results will be used by the Investigator to determine whether the subject meets criteria for randomization. For subjects in the Double-Blind Randomized Withdrawal Period of the study, the mean of the Day 64 and the Day 65 (“mean Day 64/65”) 24-hr UFC results, if available at the time of Visit R2, will be used by the Investigator to determine whether the subject should undergo Visit R3 rather than Visit R2. The Day 79 result and the Day 84 result will be used to make the initial determinations of whether the subject’s follow-up visit should be conducted at the study site or via telephone.

In addition, subjects whose Day 84 24-hr UFC is \leq ULN will collect an additional 24-hr urine sample for UFC on Day 92. This result, if available at the time the Day 98 visit is due, will also be used to determine whether the subject’s follow-up visit should be conducted at the study site or via telephone.

Subjects whose Day 92 24-hr UFC is \leq ULN should continue to be followed up and have morning serum ACTH and 24-hr UFC assessed every 2-4 weeks until their 24-hr UFC is $>$ ULN or until the Investigator and the Medical Monitor agree that the subject is stable.

Further details on sample collection and handling are provided in the Laboratory Manual.

6.10.1.2. Salivary Cortisol

Two early morning (30-45 minutes after awakening for the day) and two late night (10 PM – 12 AM; 22:00-00:00) saliva collections for salivary cortisol should be performed during the screening period within 28 days of enrollment into the open-label dose-escalation period and results reviewed for eligibility prior to enrollment. The two early morning collections should be done on different days from each other, as should the two late night collections. Subjects who require wash-out of medications should perform these collections AFTER wash-out.

During the Open-Label Dose-Escalation Period of the study, subjects will perform an early morning saliva collection and a late night saliva collection at home on Days 13, 14, 27, 28, 41, 42, 50, 51, and 56. In addition, subjects in the Double-Blind Randomized Withdrawal Period of the study will perform an early morning saliva collection and a late night saliva collection at home on Days 64, 65, 79, and 84; and subjects in the Additional Open-Label Dosing Period of the study will perform an early morning saliva collection and a late night saliva collection at home on Days 69, 70, 79, and 84. The collections that occur within 2 days before study visits should be brought to the corresponding study visit. For all other collections, when completed, a visiting nurse may assist with processing and shipping these collections to the central laboratory, or the subject may submit them to the study site, per subject preference. All saliva samples will be submitted to the central laboratory for processing.

Further details on sample collection and handling are provided in the Laboratory Manual.

6.10.1.3. Blood Hormone Levels

Levels of 11-DOC, 17-OHP, A, A4, ACTH, cortisol, DHEA, DHEAS, free T, P, renin, SHBG and total T will be measured at the central laboratory using validated methods at all study visits. Changes in hormone levels during the study will be used to assess the efficacy of ATR-101.

Further details on sample collection and handling are provided in the Laboratory Manual.

6.10.1.4. Glucose, Insulin and HbA1c

Subjects need to be fasting after 10 PM (22:00; water and maintenance medications allowed) the evening prior to Visits S1, R1/A1, and R3/A3/ET to allow for determination of fasting glucose and fasting insulin levels. Fasting glucose, insulin and HbA1c will be measured at the central laboratory using validated methods for these visits and used for calculations of insulin sensitivity. Further details on sample collection and handling are provided in the Laboratory Manual.

6.10.1.5. Lipid Panel

Subjects need to be fasting after 10 PM (22:00; water and maintenance medications allowed) the evening prior to Visits S1, R1/A1, and R3/A3/ET to allow for collection of the fasting lipid panel. Fasting lipids (total cholesterol, LDL, HDL and triglycerides) will be measured at the central laboratory using validated methods for these study visits. Further details on sample collection and handling are provided in the Laboratory Manual.

6.10.2. Pharmacokinetic Assessments

Approximately 4 mL of blood will be drawn at each sampling time point:

Table 4: Pharmacokinetic Sampling Time Points

Visit	Sampling Time Points (Morning Dose Only)
T1, T2, T3	0 (within 30 min predose), 1 (\pm 5 min), 2 (\pm 10 min), 3 (\pm 10 min) and 4 hr (\pm 10 min)
R1, R2	0 hr (trough, within 30 min predose)
R3/ET	0 hr

Logistic considerations may dictate a deviation from the specified time point; therefore, a window is permitted around each sampling time point, as shown in Table 4: sampling times up to and including 1 hr post-dose have a window of \pm 5 min and subsequent time points have a window of \pm 10 min. Actual times of sampling and actual dosing times of ATR-101 must be recorded on the eCRF. Specific collection and shipment procedures for PK samples are provided in the Laboratory Manual. All samples will be analyzed using a validated assay at a central laboratory.

PK parameters will be derived using non-compartmental methods employing WinNonlin® Phoenix version 6.3 or later (Pharsight Corp., Mountain View, CA). The following PK parameters will be estimated for ATR-101 and its major metabolites as data permit and as appropriate:

Table 5: Pharmacokinetic Parameters

C_{last}	The last quantifiable drug concentration determined directly from individual concentration-time data
C_{max}	The maximum drug concentration determined directly from individual concentration-time data
C_{max}/D	Dose-normalized C_{max} , calculated as the ratio of C_{max} to dose
T_{max}	The observed time to reach maximum concentration
AUC_{0-t}	The area under the concentration-time curve from time zero to the time of the last quantified concentration, calculated using the linear-up/log-down trapezoidal rule
AUC_{0-4}	The area under the concentration-time curve from time zero to 4 h after dosing, calculated using the linear-up/log-down trapezoidal rule
AUC_{0-4}/D	Dose-normalized AUC_{0-4} , calculated as the ratio of AUC_{0-4} to dose
λ_z	The terminal phase rate constant, estimated by linear regression through the terminal phase of the log concentration-time profile
$t_{1/2}$	The terminal phase half-life, calculated as: $t_{1/2} = \frac{\ln(2)}{\lambda_z}$
$AUC_{0-\infty}$	The area under the concentration versus time curve from time 0 to infinity (first dose only), calculated as $AUC_{0-4} + C_{last}/\lambda_z$
$AUC_{\%extrap}$	Percentage of $AUC_{0-\infty}$ extrapolated, represented as $(1 - AUC_{0-t}/AUC_{0-\infty}) * 100$
CL/F	Oral clearance calculated as: $Dose/AUC_{0-\infty}$ (Day 1 only)

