5.5. Study Drug Administration

Study drug doses should be taken approximately 12 hrs apart (twice per day dosing). The time of day that the dose is taken should be as consistent as possible (e.g., every morning at 8 AM (08:00) and every evening at 8 PM (20:00)).

Study drug should be taken immediately after consumption of food. No specific food contents are required and subjects should maintain usual eating practices. If a full meal is not possible or not aligned with a subject's usual eating practices, a light snack should be consumed prior to taking study drug.

On the morning of study visits, subjects should not take their study drug (if applicable) until directed by study site personnel. At each study visit from T1 to R2/A2, a trough PK level will be collected within 30 minutes prior to dosing and subjects will eat a breakfast prior to dose administration. See the Pharmacy Manual for more details.

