7.2.1. Visit T1 (Day 1)

At Visit T1, appropriate study site personnel should:

- Record adverse events and update medications.
- Record vital signs and weight.
- Perform a complete PE.
- Collect a urine sample for urinalysis and, if the subject is a woman of childbearing potential, perform a urine pregnancy test (preferred; or submit a serum or urine sample to a laboratory for pregnancy testing if required by your institution/IRB/EC).
- Review all inclusion and exclusion criteria to confirm that the subject is eligible for the study, including all 24-hr UFC and late night salivary cortisol levels collected within the past 28 days.

- Review the mean of all 24-hr UFC levels obtained within the past 28 days to determine the subject's 24-hr UFC stratum (1.3 to $< 4 \times$ ULN (Stratum I) or 4 to $10 \times$ ULN (Stratum II)).
- Please note that prior to enrolling the subject, regarding the laboratory values, only the Visit T1 pregnancy test (if applicable and if performed at the site), and the Visit S1 hematology, chemistry, PT, PTT, INR, HbA1c, lipid panel, serology, pregnancy test (if applicable), urinalysis, urine drug screen, 24-hr UFC, and salivary cortisol levels, need to be reviewed. The screening blood hormone levels are for baselining purposes and the results do not need to be available prior to the enrolling the subject.
- Contact the IVRS/IWRS to confirm enrollment of the subject into the open-label dose-escalation period and obtain study drug assignment.
- Collect blood samples for hematology, chemistry, hormones (11-DOC, 17-OHP, A, A4, ACTH, cortisol, DHEA, DHEAS, free T, P, renin, SHBG and total T) and PK within 30 minutes prior to administration of study drug.
 - All blood hormone collections should be performed between 6-10 AM (06:00-10:00), as close to 8 AM (08:00) as practicable.
 - Subjects need to be in a seated position for at least 15 minutes prior to collection of blood hormone levels so that renin and aldosterone levels are stable.
- Dispense open-label study drug (ATR-101 250-mg tablets) and instruct the subject on self-administration of study drug orally with food BID.
- Have the subject eat breakfast.
- Ask the subject to self-administer study drug with a nonalcoholic beverage (except grapefruit juice) while at the study site. Record the exact time of study drug administration.
- Collect plasma PK samples 1, 2, 3 and 4 hrs after administration of study drug. Record the exact time of each PK sample collection.

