9.8. Pharmacokinetics and Pharmacodynamics

9.8.1. Pharmacokinetic and Pharmacodynamic Endpoints

- The C_{max} , T_{max} , AUC, $t_{1/2}$ and other PK parameters of ATR-101 and its major metabolites (as appropriate and as the data allow)
- The relationship between C_{max} and AUC vs. the percentage change in 24-hr UFC; other PK/PD relationships may be explored as appropriate and as data allow

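### Protocol Table 5 adds Clast/λz to AUC0-4 where AUC0-t belongs, and sampling that ends 4 h after a fed dose may leave λz, t1/2, AUC0-inf and CL/F biased or not estimable (minor, secondary PK only)

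*Protocol*

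**What the plan says.** Table 4 in section 6.10.2 sets full profiles at Visits T1, T2 and T3: a predose sample, then 1 h, 2 h, "3 (\pm 10 min) and 4 hr (\pm 10 min"). Section 7.2.1 repeats this for Day 1: "Collect plasma PK samples 1, 2, 3 and 4 hrs after administration of study drug". The dose is a fed one. Section 5.5 states "Study drug should be taken immediately after consumption of food", and section 7.2.1 places the instruction "Have the subject eat breakfast" before dosing.

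Table 5 then defines the parameters:
- Clast is the last quantifiable concentration. It is not tied to 4 h.
- AUC0-t runs to the last quantified concentration, and AUC0-4 runs to 4 h. They are separate rows.
- λz is "The terminal phase rate constant, estimated by linear regression through the terminal phase of the log concentration-time profile".
- AUC0-inf is the area "from time 0 to infinity (first dose only), calculated as $AUC_{0-4} + C_{last"; the quote breaks off inside the formula, whose last term is Clast divided by λz.
- AUC%extrap is (1 − AUC0-t/AUC0-inf) × 100.
- CL/F is given as "Oral clearance calculated as" dose over AUC0-inf, on Day 1 only.

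Section 9.8.1 lists Cmax, Tmax, AUC and t1/2 "and other PK parameters of ATR-101 and its major metabolites (as appropriate and as the data allow"). Table 5 carries a similar qualifier. Section 9.8.2 names Cmax, AUC0-4 and trough levels as the PK assessments.

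**The concern.** There are two separate issues.

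The first is a formula slip. Clast/λz is the area from the time of Clast to infinity, so it has to be added to the area up to that same time, which is AUC0-t. Adding it to AUC0-4 counts the stretch between t and 4 h twice when t is before 4 h, and leaves it out when t is after 4 h. AUC%extrap, in the next row, uses AUC0-t, so the two rows do not fit together unless t is exactly 4 h.

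The second is the schedule. The Day 1 profile is the only one used for AUC0-inf and CL/F. It has four post-dose points, the last at 4 h after a meal. Three points after the peak exist only if the highest sample is the 1-h one. With a later peak, a line through 2-4 h mixes absorption with elimination and gives a half-life that is too long, or no falling slope.

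At stake are t1/2, a named PK endpoint, and the λz-based rows of Table 5, for ATR-101 and its metabolites.

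**Working it through.** The protocol states no numerical result on this point, so there is nothing to reproduce. The check is algebra plus a model whose inputs are assumptions, because the protocol gives neither a half-life nor a fed Tmax.

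**1. Formula**

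Correct form: AUC0-inf = AUC0-t + Clast/λz. Stated form minus correct form = AUC0-4 − AUC0-t.

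- Last quantifiable sample at 4.00 h: the difference is 0.
- Last sample at 3:50 or 4:10 h (the limits of the Table 4 window), absorption half-life 0.25 h, t1/2 1-8 h: +1.1% to +1.8% at 3:50, and −1.1% to −1.7% at 4:10.
- Clast at 3 h, with AUC0-4 still computed to 4 h by extrapolation:
  - absorption half-life 0.15 h, t1/2 0.5-4 h, fitted λz: +2.9% to +12.5%
  - ka 0.5-2 /h, t1/2 2-12 h, true λz: +4.9% (ka 2, t1/2 12 h) to +17.9% (ka 0.5, t1/2 2 h)

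The last two lines together give roughly 3-18%. If the 4-h value is instead set to zero and joined linearly, the excess in the first of those two sets is 2.6-7.3%.

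**2. Sampling to 4 h**

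Model: C(t) = ka/(ka − ke) × [exp(−ke·t) − exp(−ka·t)], with ke = ln 2 / t1/2 and unit dose/volume, so the true AUC0-inf is 1/ke. Samples at 0, 1, 2, 3 and 4 h; linear-up/log-down AUC0-4 as in Table 5; λz by log-linear regression on 2, 3 and 4 h.

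Worked case, ka 1 /h and true t1/2 4 h (ke = 0.1733):
- C(2) = 0.6916, C(3) = 0.6590, C(4) = 0.5826.
- For three equally spaced points the slope is [ln C(4) − ln C(2)]/2, so λz = 0.0857 and t1/2 = 0.693/0.0857 = 8.1 h.
- AUC0-4 = 2.213 and C(4)/λz = 6.80, so AUC0-inf = 9.01 against a true 5.77. CL/F is 5.77/9.01 = 0.64 of the truth, and 75% of the estimated area is extrapolated.

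Whole grid:

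| ka (/h) | True t1/2 (h) | True AUC share beyond 4 h | Highest sample (h) | Fitted t1/2 (h) | CL/F, estimate/true |
|---|---|---|---|---|---|
| 2 | 2 | 30% | 1 | 2.1 | 1.05 |
| 2 | 4 | 55% | 1 | 4.3 | 0.99 |
| 2 | 8 | 74% | 2 | 9.1 | 0.92 |
| 2 | 12 | 82% | 2 | 14.6 | 0.86 |
| 1 | 2 | 37% | 2 | 3.1 | 0.88 |
| 1 | 4 | 60% | 2 | 8.1 | 0.64 |
| 1 | 8 | 77% | 3 | 58 (fit includes a pre-peak point) | 0.18 |
| 1 | 12 | 84% | 3 | not estimable | – |
| 0.5 | 2 | 51% | 2 | 9.8 | 0.43 |
| 0.5 | 4 | 69% | 3 | not estimable | – |
| 0.5 | 8 | 83% | 4 | not estimable | – |
| 0.5 | 12 | 88% | 4 | not estimable | – |

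Only two of the twelve cases have three samples after the highest one (ka 2 /h with t1/2 2 or 4 h). In every estimable case at least 33% of the estimated AUC0-inf is extrapolated. A shorter half-life behaves better: with t1/2 1 h and absorption half-life 0.25 h, 10% is extrapolated and t1/2 is read as 1.01 h.

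**The case against.** The strongest reply is that the plan largely protects itself. When the 4-h sample is on time and quantifiable, AUC0-4 and AUC0-t are the same number and the formula is right. Actual dosing and sampling times are recorded, so a departure from 4 h is visible. The larger formula error also needs AUC0-4 to be filled in up to 4 h after a missing or unquantifiable sample, and Table 5 does not prescribe that. Table 5 and section 9.8.1 both make the parameters conditional on the data, AUC%extrap is itself a diagnostic, and rules on minimum points or an extrapolation limit are commonly left to the SAP. All of this stands, and it keeps the point small.

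A reader might infer that the half-life, AUC0-inf and CL/F from this study would simply be wrong. The document does not support that. With fast absorption (ka 2 /h) the fitted half-lives are close to modestly high, and CL/F is 0.86-1.05 of the truth. The 58-h result is not a fair forecast either: the highest sample there is at 3 h, so the fit uses a point before the peak. A regression confined to the terminal phase, as Table 5 asks, should yield no λz for that profile. Nor does any section say that these values will guide a dosing interval.

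Two things survive. The formula itself is stated without condition and contradicts the AUC%extrap row. And a general reservation about the data does not say when a falling 2-4 h line is too contaminated by absorption to report; the 8.1-h case, where the 2-h point is the observed maximum, would compute without any warning sign in the slope.

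**Conclusion.** The concern holds in a limited form, and its severity is minor. The AUC0-inf row of Table 5 names the wrong partial area. The consequence is nil with Clast at 4.00 h, about 1-2% within the sampling window, and roughly 3-18% too high if Clast is at 3 h and AUC0-4 is still taken to 4 h. CL/F moves the opposite way.

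The schedule is the larger limitation: λz, t1/2, AUC0-inf and CL/F may be biased or not estimable unless absorption is fast. The figures rest on a one-compartment model with assumed ka 0.5-2 /h and t1/2 2-12 h, under which 30-88% of the area lies beyond 4 h. The true position within that range, or outside it, cannot be settled from the protocol. Correcting the formula does not cure the truncation.

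The primary endpoint, AUC0-4 and trough levels do not depend on any of this. Cmax and Tmax are sound as long as the peak falls within the 4 h sampled.

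**What to change.** 1. In Table 5, change the formula to AUC0-inf = AUC0-t + Clast/λz. This brings it into line with AUC%extrap.
2. Either report λz, t1/2, AUC0-inf and CL/F only for profiles with at least three quantifiable points after Cmax and AUC%extrap below a stated ceiling (for example 20%), showing the number of evaluable subjects, or drop these rows from Table 5 and t1/2 from section 9.8.1. The criteria can sit in the protocol or the SAP.
3. Rest exposure on Cmax, AUC0-4 and trough, as section 9.8.2 already does. Flag profiles whose maximum is the 4-h sample, since Cmax and Tmax are then not established.

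The cost is wording only, with no extra samples or visits. The downside is that half-life and clearance may not be reported from this study: with a 20% ceiling, none of the twelve model cases above would qualify.
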